### 3.7 Description of individual procedures

#### Laboratory testing

The investigator must warn a patient to come to the scheduled study visits after fasting to have her blood sampled for laboratory testing.

**Table 2. Method and frequency of laboratory testing**

Test	Parameters	Laboratory	Method	Frequency
Blood biochemistry	Creatinine* Potassium Sodium ALT AST Total calcium Inorganic phosphorus	Site	Adopted at the hospital center	2x: visits V0 and V3
Blood biochemistry	Total calcium Inorganic phosphorus	Site	Adopted at the hospital center	3x: visits V0, and V3, V4
Hormonal blood test	Parathyroid hormone	Site	Adopted at the hospital center	1x: visit V1
Bone metabolism	Osteocalcin Ctx	Site	Adopted at the hospital center	3x: visits V1, V3, V4
	OPG RANKL	Site	Adopted at the hospital center	2x: visits V1, V4

\*Creatinine clearance (CC) is calculated by **Cockcroft-Gault** equation on visits V0 and V3:

$$\text{CrCl} = (140 - \text{age}) \times \text{IBW} / (\text{Scr} \times 0,792) \quad (\times 0.85 \text{ for females})$$

If creatinine was measured in mg/dl, to convert the value to mkmol/L it should be multiplied by 88.4.

### 3.8 Study products

Investigated products, moxonidine and bisoprolol, will be provided by the Sponsor, packaged and labeled in accordance with local regulatory requirements.

#### 3.8.1 Investigated product:

Name: I1-imidazoline receptor agonist, INN: moxonidine

Manufactured by Rottendorf Pharma GmbH, Germany, packaged and released by Abbott Healthcare SAS, France

**Pharmaceutical form:** 0.4 mg and 0.2 mg coated tablets manufactured by Rottendorf Pharma GmbH, Germany, packaged and released by Abbott Healthcare SAS, France.

One tablet contains 0.40 mg moxonidine as an active substance and the following excipients: lactose monohydrate - 95.60 mg; povidone K25 - 0.70 mg; crospovidone – 3.00 mg; magnesium stearate - 0.30 mg; hypromellose 6mPas - 1.300 mg; ethyl cellulose aqueous Disp.30% - 4.000 mg (solids 1.200 mg) ; macrogol 6000 - 0.250 mg; talc - 0.875 mg; red ferric oxide (E172) - 0.125 mg; titanium dioxide (E171) - 1.250 mg. There are 14 tablets in the blister; the carton contains 1, 2 or 7 blisters.

One tablet contains 0.20 mg moxonidine as an active substance and the following excipients: lactose monohydrate - 95.80 mg; povidone K25 - 0.70 mg; crospovidone – 3.00 mg; magnesium stearate - 0.30 mg; hypromellose 6mPas - 1.300 mg; ethyl cellulose aqueous Disp.30%- 4.000 mg (solids 1.200 mg); macrogol 6000 - 0.250 mg; talc - 0.9975 mg; red ferric oxide (E172) - 0.0025 mg; titanium dioxide (E171) - 1.250 mg. There are 14 tablets in the blister; the carton contains 1, 2 or 7 blisters.

**Posology and method of administration:** Moxonidine is taken orally, once-twice a day, regardless of meals. Maximum daily dose of moxonidine is 0.6 mg.

**Duration of treatment:** Moxonidine 0.4 mg QD is prescribed to postmenopausal patients with hypertension and osteopenia. Subsequently, in patients with no response, the daily dose is titrated up to 0.6 mg; then perindopril 10 mg may be added to the regimen at week 8, if necessary. Patients should take the medication until study week 48 (V4).

#### 3.8.2 Comparative product

**Name:** Cardioselective beta1 blocker. INN: Bisoprolol.

Produced by Merck KGaA, Germany

**Pharmaceutical form:** film-coated tablets.

One tablet contains bisoprolol hemifumarate and bisoprolol fumarate (2: 1) as active substances 5 mg, and the following excipients: calcium hydrogen phosphate anhydrous - 132 mg; corn starch fine powder - 14.5 mg; colloidal anhydrous silica - 1.5 mg; MCC - 10 mg; crospovidone - 5.5 mg; magnesium stearate - 0.97 mg, film coating: hypromellose 2910/15 - 2.2 mg; macrogol 400 - 0.53 mg; dimethicone 100 - 0.11 mg; iron oxide yellow dye (E172) - 0.02 mg; titanium dioxide (E171) - 0.97 mg.

**Posology and method of administration:** Bisoprolol is taken orally, once a day, regardless of meals.

**Duration of treatment:** Bisoprolol 5 mg is prescribed to postmenopausal patients with hypertension and osteopenia. Subsequently, in patients with no response, the daily dose is titrated up to 7.5 mg every 2 weeks; then perindopril 10 mg may be added to the regimen at week 8, if necessary. Patients should take the medication until study week 48 (V4).

### 3.8.3 Additional medications

**3.8.3.1 Name:** angiotensin converting enzyme inhibitor. INN: perindopril

Produced by Les Laboratoires Servier Industrie

**Pharmaceutical form:** film-coated tablets.

One tablet contains perindopril arginine 10 mg as an active substance. Other ingredients: lactose monohydrate, magnesium stearate, maltodextrin, hydrophobic colloidal silica, sodium starch glycolate (type A), glycerol, hypromellose, macrogol 6000, titanium dioxide (E171), copper chlorophyllin (E141 II).

**Posology and method of administration:** once a day, orally, before a meal, preferably in the morning.

**Duration of treatment:** perindopril 10 mg is prescribed to postmenopausal patients with hypertension and osteopenia who have not reached target BP (<140/90 Hgmm) by V2 (week 8). Patients should take the medication until study week 48 (V4).

**3.8.4 Name:** angiotensin II receptor blocker. INN: Losartan

Produced by Berlin-Chemie, Germany.

**Pharmaceutical form:** coated tablets.

Each tablet contains 50 mg of losartan.

**Posology and method of administration:** Bisoprolol is taken orally, once a day, regardless of meals. The product is prescribed to postmenopausal patients with hypertension and osteopenia non-responsive to moxonidine or bisoprolol monotherapy for 4 weeks and intolerant to perindopril. Patients should take the medication until study week 48 (V4).

**3.8.5. Name:** calcium and vitamin D. INN: Calcium carbonate + cholecalciferol

Produced by Nycomed Pharma, Norway.

**Pharmaceutical form:** chewable tablets.

Each tablet contains the following active ingredients calcium carbonate 1250 mg (equivalent to 500 mg of elemental calcium), cholecalciferol (vitamin D3) 5 mcg (200 IU) (as cholecalciferol concentrate - 2 mg), *excipients:* sorbitol - 390 mg; isomalt - 62 mg; povidone - 36.4 mg; magnesium stearate - 6 mg; aspartame - 1 mg; orange oil - 0.97 mg; mono- and diacylglycerols - 0.0008 mg.

**Posology and method of administration:** the product is taken orally during meals, it should be chewed or dissolve in the mouth.

### **3.9 Product packaging and storage**

#### **3.9.1 Packaging.**

Moxonidine is packaged in original factory blisters; every blister contains 14 tablets.

Bisoprolol is packaged in original factory blisters; every blister contains 10 tablets either every blister contains 50 tablets.

At every visit (V1, V2, V3), the investigator will provide a patient with the product blisters for subsequent treatment period till next visit.

**Storage conditions.** Moxonidine and bisoprolol do not require any special storage conditions.

### **3.9.2 Products counting procedures**

The investigator analyzes the patient's compliance based on the number of returned tablets at visits 2, 3 and 4.

### **3.10 Study endpoints**

#### **Primary endpoint:**

- Changes in mean values of the bone resorption marker (collagen type 1 C-telopeptide) at the end of the study (V4) from the baseline (V1) in comparison between the groups.

#### **Secondary Endpoints:**

- To assess mean values of osteocalcin at visit 4 versus baseline level (visit 1) and to compare the values between the groups
- To assess mean values of the receptor activator of nuclear factor kappa-B ligand (RANKL) at visit 4 versus baseline level (visit 1) and to compare the values between the groups
- To assess mean values of BMD at visit 4 versus baseline level (visit 1) using control dual-energy X-ray absorptiometry and to compare the results between the groups
- To assess mean telomerase activity at visit 4 versus baseline level (visit 1) and to compare the values between the groups
- To assess mean pulse wave velocity (PWV) at visit 4 versus baseline level (visit 1) and to compare the values between the groups
- To assess mean intima-media thickness (IMT) at visit 4 versus baseline level (visit 1) and to compare the values between the groups
- To estimate the proportion (%) of patients who achieved target blood pressure <140/90 mmHg at the visit 2 (Week 8), 3 (Week 24) and 4(Week 48) and according to the patient's diary.

## **4 PATIENT SCREENING AND EXCLUSION**

### **4.1 Patient Population**

Postmenopausal women with essential hypertension and osteopenia treated with moxonidine.

### **4.2 Inclusion criteria**

A patient should meet all of the following inclusion criteria:

1. Females aged 45 years and older
2. Postmenopausal (absence of menstrual periods for a minimum of 12 months) at the moment of Informed Consent sign.
3. Arterial hypertension grade I / II per ESH/ESC 2013 guidelines (diastolic pressure  $\geq 90$  and  $<110$  mm Hg, systolic pressure  $\geq 140$  and  $<180$  mm Hg).
4. Not achieving BP targets  $<140/90$  mmHg either during antihypertensive therapy or naive.
5. Absence of moxonidine or bisoprolol treatment at least 6 months before the study
6. Osteopenia of lumbar spine and/or proximal part of the femur (osteoporosis T-score from -1 to -2.5 standard deviations [SD]) by X-Ray densitometry.
7. Signed informed consent form to participate in the program.

### **4.3 Exclusion criteria**

A patient must not meet any of the following exclusion criteria:

1. Hypersensitivity to moxonidine, bisoprolol or any other ingredient of the respective formulations
2. Any Contraindications for moxonidine, bisoprolol
3. Osteoporosis (T-score below - 2.5 SD).
4. Primary or secondary hyperparathyroidism.
5. Paget's disease of bones.
6. History of low traumatic bone fractures.
7. Malabsorption syndrome.
8. History of gastro-intestinal surgery.
9. Severe disturbance of peripheral circulation.
10. Raynaud's disease.
11. Symptomatic (secondary) hypertension (caused by any primary internal diseases)

12. Morbid obesity (BMI over 40 kg/m^2).
13. Symptoms of estrogen deficiency such as hot flushes, night sweats, vaginal dryness
14. Administration of any hormone-replacement therapy (HRT) or intake of isoflavones
15. Secondary hypogonadism.
16. Systolic BP  $\geq$ 180 mm Hg and/or Diastolic BP  $\geq$ 110 mm Hg.
17. Clinical presentations of cardiovascular disease: coronary heart disease (CHD), history of stroke, transient ischemic attack (TIA), Charcot's syndrome.
18. Severe heart failure.
19. Hemodynamically significant congenital heart disease.
20. Heart rhythm disorders which require permanent use of any antiarrhythmic medications (including  $\beta$ -adrenoblockers and calcium antagonists).
21. Diabetes mellitus of any genesis.
22. Severe liver failure.
23. Severe kidney failure including patients on dialysis
24. Thyroid diseases accompanied by functional disorders (thyrotoxicosis or uncompensated hypothyroidism).
25. Alcohol and drug abuse.
26. Patients with oncological diseases diagnosed within 5 years before IC execution.
27. Inability of the patient to comprehend the essence of the program and to provide his/her consent for participation in the program.
28. Patients with any condition, which in the opinion of the Investigator makes the patient unsuitable for inclusion based on clinical judgment.
29. Corticosteroid therapy
30. Participation in any other clinical study during the whole course of this investigation including participation in a study within 30 days prior to providing the informed consent for this trial

#### **4.4 Start of treatment criteria**

Start of investigated treatment (i.e., patient enrollment to the study) is possible when all of the following conditions are met during the enrollment visit:

1. Patient is to meet all the inclusion criteria and should lack any of the exclusion criteria.

2. Patients previously treated with antihypertensive agents have undergone 7-10-day washout period according to the protocol (all antihypertensive drugs are discontinued, except fast-acting agents to relieve hypertensive episodes).

#### **4.5 Study withdrawal criteria**

A patient may be withdrawn from the study before the treatment is started, if the investigator discovers deviations from any inclusion criteria, exclusion criteria, or criteria for the treatment initiation. Patients who withdrew before the treatment start (i.e., during screening or washout period), will be substituted with new patients.

In the present study, withdrawal from the study will also mean discontinuation of the investigated treatment.

The patient may be withdrawn from the study due to the following reasons:

1. Withdrawal of the informed consent to participate in the study.
2. Low treatment compliance (<80%).
3. Adverse events that in the investigator's opinion make the treatment continuation impossible, dangerous, or inconsistent with best patient interest and safety. A SAE is not necessarily the cause of early patient withdrawal from the study.
4. According to the investigator, continued participation of the patient in the study threatens the patient's safety.
5. It is necessary to administer treatment prohibited by the study protocol.
6. Failure of the investigated treatment (i.e., recurrent rise of blood pressure  $\geq 180/120$  mmHg after previously achieved target BP level).
7. Death of the patient.
8. Sponsor decision.

#### **4.6 Early withdrawal procedures**

All patients who were withdrawn from the study early are asked to complete the final visit procedures, if possible. If the decision to terminate the patient participation was made between two scheduled visits, the patient is asked to come for the upcoming scheduled visit, as usual, or make an unscheduled visit.

The reason for the early withdrawal should be indicated in the source documents. If the patient is lost to follow-up, the investigator should make all reasonable efforts to contact the

patient to obtain information on date of withdrawal and reason for the investigated product discontinuation. If the patient cannot be reached, she will be considered as lost to follow-up.

In the case of early investigated product discontinuation due to an adverse event (regardless of whether the event should be immediately reported), the researcher must make every effort to collect information regarding the AE outcome. This information is added to the source documents and CRF, under adverse events section.

## **5 Treatment of patients**

### **5.1 Prescribed treatment**

#### **Treatment assignment at the study visits**

**Washout period** is designed for patients who have already been taking antihypertensive medications. All antihypertensive medications are discontinued 7-10 days prior to the enrollment visit. The patient is asked to refrain from taking these and any other antihypertensive medications during the washout period. The average duration of the washout period is 7 days. The investigator may shorten the duration of the washout period, but it should not be shorter than 6 half-life periods ( $T_{1/2}$ ) of the antihypertensive medications patient was taking.

During the washout period, the patient may be administered with fast-acting agents to relieve hypertensive episodes (at the investigator's discretion – nifedipine, captopril). The period from the last dose of these antihypertensives to the enrollment visit must be at least 6  $T_{1/2}$  of these agents (e.g., 18 hours for nifedipine).

If the above conditions are not met, the patient is withdrawn from the washout period and will not participate in the study. The researcher may at any time terminate the washout period, if the patient does not tolerate it well.

The washout period is not required for patients who were not previously treated with antihypertensives, and patients who were not receiving antihypertensives at the time of the screening. If the patient was treated with any antihypertensives earlier and discontinued the medications **before** the screening, the washout period is not necessary for her, if the period between the last dose of the antihypertensives and the enrollment visit is not shorter than 6  $T_{1/2}$  of these drugs.

**All enrolled patients** are randomized in the two study groups (moxonidine group or bisoprolol group).

**All group 1 patients** are prescribed with moxonidine 0.4 mg monotherapy. At the **V1 enrollment visit**, the patient will be given the medication and will take first dose of moxonidine in the presence of the investigator. Thereafter, patients will take the medication every morning, during the entire study. The medication will be dispensed to a patient at visits V1, V2, V3, and the patient will start taking the drug on her own on the day following the visit. One tablet of the investigated product should be taken daily, in the morning, regardless of meals.

On 2nd week telephone visit, the investigator evaluates efficacy, safety and tolerability of the investigated treatment. Patients will continue taking moxonidine 0.4 mg QD until next visit V2. If BP control is insufficient, the investigator may increase moxonidine dose to 0.6 mg QD.

On 4th week telephone visit, the investigator evaluates efficacy, safety and tolerability of the investigated treatment. Patients will continue taking moxonidine 0.4 mg (0.6 mg) QD until next visit V2. If BP control is insufficient with moxonidine 0.6 mg QD, the investigator adds perindopril 10 mg QD.

**All group 2 patients** are prescribed with bisoprolol 5 mg monotherapy. At the **V1 enrollment visit**, the patient will be given the medication and will take first dose of bisoprolol in the presence of the investigator. Thereafter, patients will take the medication every morning, during the entire study. The medication will be dispensed to a patient at visits V1, V2, V3, and the patient will start taking the drug on her own on the day following the visit. One tablet of the investigated product should be taken daily, in the morning, regardless of meals.

On 2nd week telephone visit, the investigator evaluates efficacy, safety and tolerability of the investigated treatment. Patients will continue to take bisoprolol 5 mg until visit V2. If BP control is insufficient, the investigator will increase bisoprolol dose to 7.5 mg QD.

On 4th week telephone visit, the investigator evaluates efficacy, safety and tolerability of the investigated treatment. Patients will continue to take bisoprolol 5 mg (7.5 mg) until next visit V2. If BP control is insufficient with bisoprolol 7.5 mg QD, the investigator adds perindopril 10 mg QD.

**At visit V2:**

- If a patient responds to the selected treatment regimen (BP <180/120 mmHg), the investigator will continue this regimen until the next visit.
- If a patient does not respond to the selected treatment regimen (BP  $\geq$ 180 /120 mmHg), the patient is withdrawn from the study.

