Group 2 will receive bisoprolol with the dose titrated to a maximum, and then, if necessary, the patient will be shifted to the combination therapy (Step 2 – adding an ACE inhibitor).

After randomization to moxonidine and bisoprolol groups (V1), patients start treatment with 0.4 mg moxonidine QD or 5 mg bisoprolol QD. If the target BP (<140/90 mmHg) is reached in 2 weeks, the patient continues taking the medication at the same dose. If the target BP is not reached in 2 weeks, the moxonidine dose is increased to 0.6 mg QD, the dose of bisoprolol is increased to 7.5 mg QD. If the target BP is not reached in 2 weeks of treatment with the increased doses, an ACE inhibitor (perindopril) at a dose of 10 mg/day is added at the 8th week of the study. In case of intolerance to perindopril, losartan at a dose of 50 mg/day will be administered.

During the study, the patient will have parameters of efficacy, tolerability and safety of the therapy with moxonidine or bisoprolol regularly assessed.

The study design is shown in Figure 1.

Figure 1. The overall study design

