### 3.4 Schedule of the study procedures

Prior to the study enrollment, examination to assess conformity with the inclusion/exclusion criteria, to obtain baseline data and ensure washout period (if necessary) will be carried out for a patient. After enrollment and initiation of the investigated treatment, the study procedures will be conducted to assess product tolerability, safety, efficacy and patient compliance. All scheduled visits are mandatory. Washout period will be carried out only for patients with prior antihypertensive therapy. Each patient is to sign the informed consent prior to any study activities including screening / “examination to assess conformity with the in- and exclusion criteria.

Schedule of the study procedures is presented in Table 2.

	Visit 0 Screening	Visit 1	Visit 2	Visit 3	Visit 4
	Day-14...-1	Day 0	Week 8	Week 24	Week 48
Drug administration		+	+	+	+
Dose titration / treatment adjustment		+	+	+	
BP / HBR / Patients' diary analysis	+	+	+	+	+
ECG, K, Na	+			+	
Creatinine	+			+	
ALT/AST	+			+	
Parathyroid hormone	+				
X-ray densitometry, BMD	+				+
Total calcium, Phosphorus	+			+	+
PWV		+			+
IMT + evaluation of subclinical atherosclerosis		+			+
Telomerase activity		+			+
Osteocalcin		+		+	+
Collagen type 1 C-telopeptide		+		+	+
Osteoprotegerin, RANKL		+			+
Safety Information	+	+	+	+	+

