### **3.6.3 Telephone visits (TV1 and TV2)**

Telephone visits are conducted at week 2 and week 4 after the enrollment visit. The investigator will document the disease history since the last visit, including all adverse events and changes in concomitant treatment.

On the 2nd week telephone visit (**TV1**), the investigator evaluates efficacy, safety and tolerability of the investigated treatment. Patients will continue to take moxonidine 0.4 mg/bisoprolol 5 mg until visit V2. If BP control is insufficient, the investigator may increase moxonidine and bisoprolol doses to 0.6 mg and 7.5 mg QD, respectively.

On the 4th week telephone visit (**TV2**), the investigator evaluates efficacy, safety and tolerability of the investigated treatment. Patients will continue to take moxonidine 0.6 mg/bisoprolol 5 mg until visit V2. If BP control is insufficient with moxonidine 0.6 mg/bisoprolol 7.5 mg QD, the investigator adds perindopril 10 mg QD.

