### **3.6.4 Visit 2 (V2)**

Visit 2 is conducted at week 8 after the enrollment visit. The investigator will document the disease history since the last visit, including all adverse events, changes in concomitant treatment, and changes in concomitant medications doses, if any.

The investigator will analyze the effectiveness of the therapy according to the patient's BP self-monitoring diary data.

The investigator measures blood pressure and heart rate in a sitting position after 5 minutes of rest. **Two** measurements are done; the average value of the measurements is documented. BP is measured on the same arm during the entire study.

The investigator analyzes the patient's compliance based on the number of returned tablets.

The investigator evaluates response to the treatment (target BP reaching), documents it in source documents and decides on further treatment of the patient. If target BP has not been reached, the patient's investigated product dose is titrated according to the study design. If the target BP has been reached, the patient continues with the current treatment until the next visit.

The investigator will invite the patient to the next visit (visit V3) scheduled for week 24 after the enrollment visit (168 days  $\pm$  5 days after the enrollment visit); the patient will be asked to return the investigated medication blisters (empty, started and not started blisters). The patient will be instructed to start taking the provided product the next day morning, 1 tablet per day. The patient will be instructed to report any adverse events (if applicable) to the investigator.

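### At V2 and V3, section 5.1 continues treatment at any BP below 180/120 while 3.6.4 and 3.6.5 titrate to below 140/90; the week 2 and perindopril steps are also stated inconsistently

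*Combined protocol and SAP*

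**What the plan says.** **Visits V2 and V3.** Section 5.1 reads: "If a patient responds to the selected treatment regimen (BP <180/120 mmHg), the investigator will continue this regimen until the next visit". Its other branch, at or above 180/120, is withdrawal from the study. The text for V3 is the same. Section 3.6.4 says of V2: "If target BP has not been reached, the patient's investigated product dose is titrated according to the study design". Section 3.6.5 repeats this for V3. Section 3.1 sets the target at below 140/90 mmHg. Section 3.8.3 prescribes perindopril to women who have not reached that target by V2. The schedule in 3.4 marks the row "Dose titration / treatment adjustment" at V1, V2 and V3, without a BP threshold.

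**Week 2.** The synopsis and 3.1 increase the dose in both arms if target is not reached. Section 3.6.3 leaves this to the investigator in both arms. Section 5.1 differs by arm. For moxonidine: "If BP control is insufficient, the investigator may increase moxonidine dose to 0.6 mg QD". For bisoprolol: "If BP control is insufficient, the investigator will increase bisoprolol dose to 7.5 mg QD".

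**Perindopril.** Section 3.1 says that perindopril "at a dose of 10 mg/day is added at the 8th week of the study". The synopsis and 3.8.1 to 3.8.3 also give week 8. At the week 4 telephone visit, however, 3.6.3 says: "If BP control is insufficient with moxonidine 0.6 mg/bisoprolol 7.5 mg QD, the investigator adds perindopril 10 mg QD". Section 5.1 does the same at week 4, by arm; for moxonidine: "If BP control is insufficient with moxonidine 0.6 mg QD, the investigator adds perindopril 10 mg QD".

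**The concern.** Section 5.1 is headed as the prescribed treatment, so an investigator would look there for the dosing rule. At V2 and V3 it offers only continuation or withdrawal. An investigator who follows 3.6.4 or 3.6.5 escalates the same woman.

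Two things are at stake. The first is patient care: a woman can remain hypertensive for months with a permitted step unused. Short-acting agents are allowed for episodes (5.2), but they do not replace titration, and 5.4.2 bars other antihypertensives outside the study regimen.

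The second is the meaning of the BP endpoint. The proportion below 140/90 at V2, V3 and V4 is a secondary endpoint, compared between groups (6.2, item 7). In an open-label trial, dose and perindopril exposure would depend partly on which section was followed. The perindopril start matters for V2 in particular. If it starts at week 4, some women have had four weeks of combination therapy by V2. If it starts at week 8, V2 describes monotherapy.

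**Working it through.** The plan states no figure for this point, so the check compares texts and then computes visit intervals.

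**1. The two rules applied to the same woman.** Take a woman above 140/90 but below 180/120 at the visit, with a step unused.

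| Section | V2 | V3 |
|---|---|---|
| 5.1 | continue unchanged | continue unchanged |
| 3.6.4 / 3.6.5 | titrate | titrate |
| 3.8.3 | perindopril | silent |
| 3.4 schedule | titration marked, no threshold | titration marked, no threshold |
| 10.3 definition | non-responder | non-responder |

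Entry requires systolic 140 to below 180 and diastolic 90 to below 110 (4.2). Every woman is therefore below 180/120 at entry, and one whose BP has not changed at all counts as responding under 5.1.

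**2. Who still has a step left at V2 or V3.** Sections 3.6.3 and 5.1 do titrate by telephone at weeks 2 and 4, so a woman already on perindopril is outside the problem. Those inside it are:
- women whose perindopril is held to week 8, as 3.1 and 3.8 direct, and who are then managed by 5.1 at V2;
- women still on the starting dose and above target at week 4, because the week 4 text names a step only for those already on 0.6 mg or 7.5 mg;
- women who lose control after week 4.

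**3. Time without escalation.** Inputs: V2 at day 56 (3.6.2), V3 at day 168 (3.6.4), V4 at day 336 (3.6.5), each plus or minus 5 days. Gap in weeks = (later day − earlier day) / 7. Two visit windows together add or remove up to 10 days.
- V2 to V3: (168 − 56) / 7 = 112 / 7 = 16 weeks; with windows 102/7 to 122/7 = 14.6 to 17.4.
- V3 to V4: (336 − 168) / 7 = 168 / 7 = 24 weeks; with windows 158/7 to 178/7 = 22.6 to 25.4.
- V2 to V4: (336 − 56) / 7 = 280 / 7 = 40 weeks; with windows 270/7 to 290/7 = 38.6 to 41.4.

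The 16 weeks apply if 5.1 is followed at V2 only, the 24 weeks if at V3 only, and the 40 weeks if at both.

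**4. Perindopril timing.** 8 − 4 = 4 weeks between the two stated starts.

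**5. Week 4 doses.** The continuing doses named in 3.6.3 are moxonidine 0.6 mg and bisoprolol 5 mg: the raised dose in one arm and the starting dose in the other. Section 5.1 names both dose levels in both arms, so 3.6.3 looks like a slip.

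**The case against.** The best defence is that 5.1 is only a safety stop. Under the treatment regimens heading in 3.6.2, each arm's regimen includes titration to the maximum and then an ACE inhibitor if needed. Continuing the regimen could then mean staying on that stepped plan, with 180/120 as the withdrawal limit; 4.5 item 6 uses the same pair of values for treatment failure. Sections 3.6.4 and 3.6.5 would apply unchanged. This may well be what was intended, but the wording does not carry it. Section 5.1 ties response to a level that every woman meets at entry, directs continuation until the next visit, and has no titration branch.

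Other parts of the defence stand and limit the point:
- A reader might infer that the week 2 step is optional for moxonidine, so that many women would reach V2 on the starting dose. The documents do not settle that: the synopsis and 3.1 make the increase mandatory in both arms. The softer wording in 3.6.3 and 5.1 is a further conflict, not the governing rule.
- The schedule gives no threshold, and 3.8.3 speaks to V2 only. At V3 the only BP-triggered text against 5.1 is 3.6.5, which speaks of the investigated product's dose. For a woman already on 0.6 mg or 7.5 mg, a perindopril start at V3 must be inferred from its reference to the study design.
- The trial is exploratory, its efficacy results are to be presented descriptively (10.3), and BP response is secondary.

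**Conclusion.** The plan is wrong as written and should be corrected before use. Sections 5.1 and 3.6.4/3.6.5 give incompatible instructions at V2 and V3, and the week 2 step and perindopril start are each stated in more than one way.

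The size is 16, 24 or 40 weeks without escalation per affected woman, plus a 4-week difference in perindopril start. These intervals assume nominal visit days, BP above target and below 180/120, a step still unused, and an investigator who follows 5.1. The 24-week case also relies on the inference about perindopril at V3 when the woman is already on the higher dose. The number of women affected cannot be derived from the documents.

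A reader might go further and infer a biased CTX comparison or widespread non-escalation. Neither is supported: no link from these rules to CTX is shown, and the telephone visits at weeks 2 and 4 do provide titration.

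**What to change.** 1. In 5.1, at V2 and V3: continue if BP is below 140/90. Otherwise take the next unused step: 0.6 mg or 7.5 mg, then perindopril 10 mg, or losartan 50 mg if perindopril is not tolerated. Keep 180/120 only as the withdrawal threshold. This also makes a perindopril start at V3 explicit.
2. State one perindopril start time in the synopsis, 3.1, 3.6.3, 3.8 and 5.1. Week 8 is the smaller edit: most sections already give it, and it coincides with a clinic visit, whereas week 4 is a telephone contact.
3. Make the week 2 increase mandatory in both arms in 3.6.3 and 5.1, as 3.1 has it. At week 4, add the dose increase for a woman above target on the starting dose. Correct the unequal week 4 doses in 3.6.3.

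The cost is rewording in those sections. No visit, measurement or change to the analysis is needed.
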